7.2. Definition of Dose-Limiting Toxicity:**DLT time frames:**

- Group 1: The time frame for DLT assessment will be within 29 days of therapy initiation in the ipilimumab/BMS-986156 group

Group 2: within 43 days of therapy initiation in the sequential arm (ipilimumab/BMS-986156/radiation)

- Group 3: within 29 days of therapy initiation in the nivolumab/BMS-986156 concurrent group
- Groups 1 (ipilimumab + BMS-986156) and 2 (ipilimumab + BMS-986156 + radiation): Patients will get DLT assessments done every other week (14 ± 3 days after the drug infusion) during the DLT period. When patient is unable to make a clinic visit, a visit to a local healthcare provider must be done for DLT assessment. A report and lab test results must be provided to the trial treating physician or to the trial PI. This will be done case by case in association with the local physician of the patient.

7.2.1. Dose Limiting Toxicity (DLT):

DLT is defined as any:

Group 1 DLT definition:

- Any ≥ Grade 3 bronchospasm or other hypersensitivity reactions lasting for >6h;
- Any other ≥ Grade 3 non-skin related adverse event with the exception of laboratory abnormalities that is asymptomatic, not requiring hospitalization, responsive to supplementation within 24 hours).
- Any Grade 4 laboratory abnormalities, except AST, ALT, or total bilirubin;
 - AST or ALT > 8 x ULN,
 - Total bilirubin > 5 x ULN;
 - AST or ALT > 3 x ULN AND Total Bilirubin > 2 X ULN (Potential drug-induced liver injury as defined by Hy's Law)
- Grade 3/4 rash if no improvement (i.e. resolution to ≤Grade 1) after a 1-2 week infusion delay. Use of topical steroids is permitted.
- Any other Grade 4 adverse event;
- Any adverse event, laboratory abnormality or intercurrent illness which, in the judgment of the investigator, presents a substantial clinical risk to the subject with continued study drug dosing;
- Any motor neurologic toxicity ≥ Grade 3 regardless of causality;
- Any ≥ Grade 3 treatment-related sensory neurologic toxicity.
- Combination related toxicity, such as infusion reactions, diarrhea, colitis, etc., that prevents administration of ipilimumab/BMS-986156 for > 21 days and/or nivolumab/BMS-986156 for > 28 days from the scheduled dose.

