7.3. Duration of Therapy and Criteria for Treatment Delay

7.3.1. Duration of Therapy:

In the absence withholding treatment cycles due to adverse events, study treatment will be continued for the full 4 Ipilimumab/BMS-986156 cycles, followed by 26 cycles of Nivolumab (group 1 and 2). Nivolumab/BMS-986156 will be given for 4 cycles, followed by 22 cycles of Nivolumab (group3). Nivolumab will be given for a total of 26 cycles on all groups.

7.3.2. Criteria for Treatment Delay:

Patients will delay treatment with ipilimumab/BMS-986156 or nivolumab/BMS-986156 if they experience at least one of the following adverse events considered by the Investigator to be “possibly”, “probably” or “certainly” related to trial drug treatment with or without SBRT treatment:

- Any Grade 3 non-skin related adverse event (excluding alopecia, and Grade 3 nausea, vomiting, and diarrhea for which adequate supportive therapy has been instituted)
- Any Grade 3 skin-related adverse event (including irAEs)
- Any of the Grade 4 hematologic adverse events for >7 days
- Grade 3 fatigue only if ≥ 7 days
- SBRT scheduling conflicts or machine maintenance issues

7.3.3. Criteria for Restart of Ipilimumab/BMS-986156 or nivolumab/BMS-986156 Treatments:

Patients requiring delay or cessation of treatments of trial drugs based on the judgment of the attending physician can be restarted as long as:

- The adverse event is not listed in 7.2.1, and:

- If the adverse event has resolved to \leq Grade 1 severity or returns to baseline within 4 weeks (28 days) of dose administration, treatment will be restarted \geq 4 weeks from the last dose administration, to complete dosing regimen outlined above.
- If the adverse event has not resolved to \leq Grade 1 severity or returned to baseline in the protocol-specified dosing window (3 weeks, for ipilimumab/BMS-986156; 4 weeks for nivolumab/BMS-986156), the next scheduled dose will be omitted and remaining doses will be administered if approved by the Principal Investigator.
- For ipilimumab/BMS-986156: Treatment delays for reasons other than adverse events (e.g. for scheduling conflicts or SBRT machine maintenance issues) are allowed as long as all four 3 week cycle ipilimumab/BMS-986156 doses are given within 8 months. In this scenario, all 4 doses should be administered separated by a minimum interval of 3 weeks.

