7.3.4. Criteria for Permanent Discontinuation of Ipilimumab/BMS-986156 or nivolumab/BMS-986156

Patients who demonstrate signs of progression of disease prior to completion of Ipilimumab/BMS-986156 or Nivolumab/BMS-986156 may continue on trial if determined to provide clinical benefit per the treating physicians and/or PI's discretion.

- Patients will continue to be monitored with visits or phone calls (if patient is unable to arrive) as discussed in section 9.1.3 but will no longer receive further treatment if:
- Patients suffer any of the following adverse events with at least a possible, probable or definite attribution to study treatments:*Adverse event(s) considered related to study treatments as described below:*
 - Any \geq Grade 2 eye pain or reduction of visual acuity that does not respond to topical therapy and does not improve to Grade 1 severity within 2 weeks of starting therapy OR requires systemic treatment;
 - Any \geq Grade 3 bronchospasm or other hypersensitivity reaction;
 - Any other \geq Grade 3 non-skin related adverse event with the exception of laboratory abnormalities;
 - Any Grade 4 laboratory abnormalities, except AST, ALT, or total bilirubin;
 - AST or ALT \geq 8 \times ULN,
 - Total bilirubin \geq 5 \times ULN;
 - Any other Grade 4 adverse event;
 - Drug related toxicity that prevents administration of ipilimumab/BMS-986156 for \geq 21 days or nivolumab/BMS-986156 for 14 days from the scheduled dose
- Any adverse event, laboratory abnormality or intercurrent illness which, in the judgment of the investigator, presents a substantial clinical risk to the subject with continued study drug dosing;
- Subject experiences an allergic/infusion reaction while receiving study drug at a slower infusion rate due to a prior allergic/infusion reaction;
- Any motor neurologic toxicity \geq Grade 3 regardless of causality;

- Any \geq Grade 3 treatment-related sensory neurologic toxicity.
- Drug related toxicity that prevents administration of ipilimumab for \geq 21 days from the scheduled dose

Exceptions to Permanent Discontinuation of ipilimumab dosing:

- Hospitalization for \leq Grade 2 adverse events where the primary reason for hospitalization is to expedite the clinical work-up;

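### Sections 7.2.1 and 7.3.2 to 7.3.4 (with 5.1.18 and 5.1.19) give conflicting delay, restart and discontinuation instructions for some related Grade 3 non-skin, non-laboratory events and for some delay lengths

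*Combined protocol and SAP*

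**What the plan says.** **Delay (7.3.2).** Treatment is delayed for events judged possibly, probably or certainly "related to trial drug treatment with or without SBRT treatment". The list includes "Any Grade 3 non-skin related adverse event (excluding alopecia, and Grade 3 nausea, vomiting, and diarrhea" (the last three when adequately supported) and, as a separate item, "Grade 3 fatigue only if ≥ 7 days".

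**Restart (7.3.3).** A delayed patient may restart provided "The adverse event is not listed in 7.2.1" and the event resolves to Grade 1 or lower, or to baseline, within 28 days. If it has not resolved within the dosing window (3 weeks for ipilimumab/BMS-986156, 4 weeks for nivolumab/BMS-986156), the next dose is omitted and later doses may be given with Principal Investigator approval. For nivolumab/BMS-986156 the investigator may also extend a delay case by case. One example given is a long steroid taper for a drug-related event that is not a DLT.

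**DLT list (7.2.1).** For all groups the list includes any other event of at least "Grade 3 non-skin related adverse event with the exception of laboratory abnormalities that is asymptomatic, not requiring hospitalization" and responsive to supplementation within 24 hours. A later item on Grade 3 non-hematologic toxicity carries exceptions, among them endocrinopathy well controlled by hormone replacement, isolated fever, tumor flare, and fatigue of 7 days or less. Toxicity that prevents dosing for more than 21 days (ipilimumab/BMS-986156) or more than 28 days (nivolumab/BMS-986156) is also a DLT.

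**Permanent discontinuation (7.3.4).** With at least possible attribution, treatment ends for any other event of at least "Grade 3 non-skin related adverse event with the exception of laboratory abnormalities". It also ends when related toxicity prevents dosing for 21 days or more (ipilimumab/BMS-986156) or for 14 days (nivolumab/BMS-986156). The only exception concerns hospitalization for events of Grade 2 or lower.

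**Ipilimumab section (5.1.18 and 5.1.19).** Section 5.1.18 mentions a possible second 21-day withholding, then says that withholding beyond 21 days leads to permanent discontinuation. Section 5.1.19 lets dosing resume after resolution to Grade 1 or baseline, and for endocrinopathies controlled with chronic therapy. It sets no grade limit.

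**The concern.** Sections 7.3.2 and 7.3.4 use nearly the same words at effectively the same attribution threshold, but one leads to a hold and the other to a permanent stop. Nothing says which prevails. Two investigators faced with the same event could act differently and both cite the protocol.

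This is first a patient-safety matter. It also affects the analysis. Safety and toxicity are the primary objectives, and 3.1.1 points to section 7.3 for the trial's safety rule. If the stopping instruction depends on which section is read, then drug exposure, discontinuation rates and the toxicity that can still be observed afterwards depend on it too. Differences between groups of about 20 patients could then partly reflect how the rule was read.

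**Working it through.** No sample-size or power figure is involved. The check follows each class of related Grade 3 non-skin event through the four sections.

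| Event class (related, Grade 3) | 7.3.2 | 7.2.1 and 7.3.3 | 7.3.4 | Result |
|---|---|---|---|---|
| Non-laboratory, on the DLT list, no exception applies | Delay | Listed, so no restart | Stop | Outcomes converge; only the delay label conflicts |
| DLT exception: controlled endocrinopathy, isolated fever, tumor flare | Delay | Restart possible if the exceptions override the general Grade 3 item | Stop | Direct conflict |
| Nausea, vomiting or diarrhea with adequate support | Exempt from delay | Restart does not arise | Stop, read literally | Direct conflict |
| Fatigue under 7 days | Fatigue item not met | Restart does not arise on that item | Stop, read literally | Direct conflict on the fatigue item |
| Laboratory abnormality | Delay | Restart possible if not a DLT | Excluded from the Grade 3 item | Generally no conflict; AST/ALT and bilirubin have their own thresholds |

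*Second row.* The exceptions in 7.2.1 are attached to the later non-hematologic item, while the general Grade 3 non-skin item stands alone earlier in the list. If the general item prevails, restart is barred and 7.3.3 agrees with 7.3.4, but the exceptions then do nothing for these events. If the exceptions prevail, 7.3.3 permits restart and 7.3.4 forbids it. For controlled endocrinopathy, 5.1.19 independently lets ipilimumab resume, so that case conflicts with 7.3.4 on either reading.

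*Fatigue.* The general Grade 3 item in 7.3.2 does not name fatigue among its exclusions. The row relies on the specific fatigue item, which would be redundant if the general item already covered shorter episodes.

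*Delay length, counted from the scheduled dose:*

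| Regimen | 7.3.4 stops at | 7.2.1 calls it a DLT at | 7.3.3 route |
|---|---|---|---|
| Ipilimumab/BMS-986156 | 21 days or more | more than 21 days | Omit one dose, then continue with approval; cycle is 21 days |
| Nivolumab/BMS-986156 | 14 days | more than 28 days | Omit one dose, then continue with approval, or extend the delay; cycle is 28 days |

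If one dose is omitted and the next is given on its nominal date, the gap from the omitted dose equals one cycle. For ipilimumab/BMS-986156 that is 21 days, which meets the 21-day stop in 7.3.4 but is not over 21 days in 7.2.1. Using the 3-day window, a dose at 21 − 3 = 18 days would stay under the limit. For nivolumab/BMS-986156 the gap is 28 days, or 28 − 3 = 25 at the early edge. Both exceed 14 days, and neither exceeds 28. On the nominal schedule, then, the omit-and-continue route in 7.3.3 reaches the stop in 7.3.4 for both regimens. For nivolumab/BMS-986156, a delay caused by related toxicity and lasting from 14 to 28 days ends treatment under 7.3.4, is not a DLT by duration under 7.2.1, and may be extended under 7.3.3.

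**The case against.** The strongest reply is that the sections work in sequence: hold the dose (7.3.2), check the DLT list (7.3.3), and stop if the event is on it (7.3.4). Because 7.2.1 lists Grade 3 non-skin events generally, most such events end in the same place. A hold followed by a bar on restart does not contradict discontinuation. Laboratory abnormalities are also largely handled consistently, because 7.3.4 leaves them out of its Grade 3 item. Both points stand. A reader might infer that every related Grade 3 non-skin event carries two opposite instructions, and the documents do not support that.

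The sequence does not settle the rest. It fails where 7.2.1 makes exceptions that 7.3.4 does not repeat, where 7.3.2 exempts an event that 7.3.4 does not, and where the day limits differ.

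A reader might also size the problem from the 34% rate of grade 3 treatment-related toxicity in the earlier ipilimumab-plus-SBRT trial (section 3.3): 60 × 0.34 = 20.4 patients. That does not hold either. Group 1 has no SBRT and Group 3 has no ipilimumab. The 34% is not broken down, so skin and laboratory events cannot be removed from it, nor can events for which the rules converge. Nor do the documents show that these are the events most likely to occur: adverse events with BMS-986156, alone or with nivolumab, are described as mainly Grade 1 and 2.

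Finally, the organ-specific algorithms in Appendix B are figures that are not reproduced in the text reviewed. They may give event-level guidance, but they could not be checked.

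**Conclusion.** Wrong as written, within limits. The instructions conflict for three sets of cases: the DLT exceptions in 7.2.1, the events exempted from delay in 7.3.2, and delays that pass the day limits in 7.3.4 while 7.3.3 still allows dosing. For other Grade 3 non-skin, non-laboratory events on the DLT list, restart is already barred and only the delay label is at odds with 7.3.4.

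No count of affected patients can be derived. The events are plausible: at ipilimumab 3 mg/kg, section 5.1.8 reports Grade 3/4 immune-related endocrine events in 0.9-3.8% of patients and gastrointestinal events in 4.5-7.6%. The documents do not say how many were hormone-controlled or adequately supported.

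The first conflict assumes that the 7.2.1 exceptions override the general Grade 3 item, except for controlled endocrinopathy on ipilimumab, where 5.1.19 is enough. The second assumes that 7.3.4 is read literally and that the specific fatigue item governs fatigue. The third uses nominal cycle lengths.

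**What to change.** Reconcile 5.1.18, 5.1.19, 7.2.1, 7.3.2, 7.3.3 and 7.3.4 so that each combination of event type, grade and delay length leads to one instruction, and state which section takes precedence if two apply. A single table cited by all of these sections would do this. It should say:

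- whether the 7.2.1 exceptions override its general Grade 3 item, and whether they carry over to 7.3.4;
- whether the 7.3.2 exemptions carry over to 7.3.4;
- one delay limit per regimen, with the same inequality and the same starting date throughout, and how omitted doses and extensions count against it.

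The Appendix B algorithms should be checked against the result. Which rule applies in each case is for the sponsor to decide. The cost is protocol wording only, with no change to sample size or analysis.

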7.3.4. Criteria for Permanent Discontinuation of Ipilimumab/BMS-986156 or nivolumab/BMS-986156

Patients who demonstrate signs of progression of disease prior to completion of Ipilimumab/BMS-986156 or Nivolumab/BMS-986156 may continue on trial if determined to provide clinical benefit per the treating physicians and/or PI's discretion.

- Patients will continue to be monitored with visits or phone calls (if patient is unable to arrive) as discussed in section 9.1.3 but will no longer receive further treatment if:
- Patients suffer any of the following adverse events with at least a possible, probable or definite attribution to study treatments:*Adverse event(s) considered related to study treatments as described below:*
 - Any \geq Grade 2 eye pain or reduction of visual acuity that does not respond to topical therapy and does not improve to Grade 1 severity within 2 weeks of starting therapy OR requires systemic treatment;
 - Any \geq Grade 3 bronchospasm or other hypersensitivity reaction;
 - Any other \geq Grade 3 non-skin related adverse event with the exception of laboratory abnormalities;
 - Any Grade 4 laboratory abnormalities, except AST, ALT, or total bilirubin;
 - AST or ALT \geq 8 \times ULN,
 - Total bilirubin \geq 5 \times ULN;
 - Any other Grade 4 adverse event;
 - Drug related toxicity that prevents administration of ipilimumab/BMS-986156 for \geq 21 days or nivolumab/BMS-986156 for 14 days from the scheduled dose
- Any adverse event, laboratory abnormality or intercurrent illness which, in the judgment of the investigator, presents a substantial clinical risk to the subject with continued study drug dosing;
- Subject experiences an allergic/infusion reaction while receiving study drug at a slower infusion rate due to a prior allergic/infusion reaction;
- Any motor neurologic toxicity \geq Grade 3 regardless of causality;

- Any \geq Grade 3 treatment-related sensory neurologic toxicity.
- Drug related toxicity that prevents administration of ipilimumab for \geq 21 days from the scheduled dose

Exceptions to Permanent Discontinuation of ipilimumab dosing:

- Hospitalization for \leq Grade 2 adverse events where the primary reason for hospitalization is to expedite the clinical work-up;

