- For nivolumab/BMS-986156: Extensions to the period of dose delays may be granted for individual subjects on a case by case basis decided by the Investigator in settings where benefit/risk may justify continued study therapy (e.g., subject deriving clinical benefit who requires prolonged steroid taper for management of non-DLT drug-related AEs, or experiences delays for management of a non-drug related AE).
- The end of cycle tumor assessments (i.e., CT/MRI, positron emission tomography, etc) will continue on an every 8 weeks schedule relative to the subject's 1st dose regardless of any treatment delay incurred.

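### Group 3: section 7.3.4 ends nivolumab/BMS-986156 after a 14-day toxicity hold, section 7.3.3 allows longer holds and resumption, and neither is given precedence

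*Combined protocol and SAP*

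**What the plan says.** Section 7.3.4 keeps patients under monitoring "but will no longer receive further treatment if" a listed event occurs. One listed event is drug-related toxicity that blocks "nivolumab/BMS-986156 for 14 days from the scheduled dose". The entry has no inequality sign; I read it as 14 days or more. The only exception in 7.3.4 concerns hospital admission to speed the work-up of low-grade events, and it stands under a heading that names ipilimumab dosing.

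Section 7.3.3 sets out restart. Its first condition is "The adverse event is not listed in 7.2.1, and". If an event has not settled within the dosing window, given as "4 weeks for nivolumab/BMS-986156", then "the next scheduled dose will be omitted and remaining doses will be administered if approved by the Principal Investigator". A further bullet, specific to this regimen, says: "Extensions to the period of dose delays may be granted for individual subjects on a case by case basis decided by the Investigator". It requires that benefit and risk justify continuing, and its examples include a long steroid taper for a drug-related event that is not a DLT. It states no maximum.

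Section 7.2.1 counts as a DLT any combination-related toxicity that blocks "nivolumab/BMS-986156 for > 28 days from the scheduled dose". This entry appears in the group 1 list and again in the list for groups 2 and 3.

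Group 3 combination doses fall on days 1, 29, 57 and 85, with nivolumab alone from day 113 (section 7.1.1.3). The group 3 DLT window is 29 days from the start of therapy (section 7.2).

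**The concern.** Sections 7.3.3 and 7.3.4 govern the same regimen and the same kind of event but prescribe different outcomes. Two investigators facing the same drug-related hold could act differently, one stopping for good and the other resuming. Each could cite the protocol, and each could be recorded as deviating from it.

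This bears on patient safety and on the group 3 data. The safety and toxicity profile of nivolumab/BMS-986156 with SBRT is a primary objective (section 2.1). Doses received, reasons for stopping and counts of deviations would depend partly on which section the treating team followed.

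**Working it through.** The documents state no figure to reproduce. The check is day arithmetic on the group 3 schedule, followed by a comparison of the rules.

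**Step 1. Dates for a held dose.** Let d be the scheduled day. The 7.3.4 limit is reached on d + 14. The 7.2.1 entry (more than 28 days) is first met on d + 29. If the dose is omitted, the next one is due on d + 28.

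| Held dose | d | d + 14 | d + 29 | Next dose, d + 28 |
|---|---|---|---|---|
| 2 | 29 | 43 | 58 | 57 |
| 3 | 57 | 71 | 86 | 85 |
| 4 | 85 | 99 | 114 | 113 (nivolumab alone) |

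Omitting a dose leaves 28 days between the missed dose and the next, or 25 to 31 days with the 3-day scheduling window. Either way this is more than 14.

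**Step 2. The rules applied to a held dose 2.** Take a drug-related event that is not a stopping event under another 7.3.4 entry and is not otherwise listed in 7.2.1.

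- *Unresolved on day 29, resolved on day 36.* Toxicity blocked dosing for 36 − 29 = 7 days. Section 7.3.3 omits the dose and resumes on day 57. Section 7.3.4 is not met if only the time with active toxicity counts. It is met if the whole 28-day gap counts. The text does not say which.
- *Unresolved on day 43, resolved by day 57.* Toxicity blocked dosing for 14 to 28 days. Section 7.3.4 ends treatment. Section 7.3.3 allows resumption with approval, or an extended delay. The rules conflict however the gap is counted.
- *Still unresolved on day 58.* Section 7.3.4 ends treatment. The extension bullet has no stated maximum, but a hold of more than 28 days is itself an entry in 7.2.1, and 7.3.3 bars restart for events listed there. Whether that entry applies after the DLT window has closed is not stated.

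**Step 3. The DLT window.** Dose 2 is due on day 29, when the 29-day window ends. A hold of dose 2 reaches 14 days on day 43, which is 43 − 29 = 14 days later. It exceeds 28 days on day 58, which is 58 − 29 = 29 days later. Were dose 2 scheduled 3 days early, on day 26, these dates would be 26 + 14 = 40 and 26 + 29 = 55, still after the window. The entry of more than 28 days cannot be met inside the window.

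**Step 4. Comparison with ipilimumab.** For ipilimumab/BMS-986156 the two sections use the same number: at least 21 days in 7.3.4 and more than 21 days in 7.2.1. Only the nivolumab figures diverge, 14 against 28. This does not show which figure was intended.

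**The case against.** The best defence is that the rules can coexist. The 4 weeks in 7.3.3 is the dosing interval, whereas the 14 days in 7.3.4 runs from the scheduled dose. An event that resolves a week after the scheduled day can lead to an omitted dose without meeting the 14-day limit. The extension bullet can be read as a specific exception to a general rule, since it is confined to individual patients and needs a benefit/risk case. The first argument stands for holds shorter than 14 days. It does not help from 14 days on. The second is a possible reading, but 7.3.4 does not list it among its exceptions and 7.3.3 does not say that it overrides 7.3.4.

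Three stronger readings are tempting, and the documents do not support them.

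- A reader might infer that 14 days in 7.3.4 and more than 28 days in 7.2.1 contradict each other. Section 7.2.1 defines DLTs and does not itself end treatment; it bars restart only through 7.3.3. A stopping limit may be shorter than a DLT limit.
- A reader might infer that stopping at 14 days prevents holds from being counted as DLTs, and so distorts the primary endpoint. Step 3 rules this out within the stated window, because both limits fall after it. In addition, 7.2.1 restricts the DLTs that define the MTD in groups 2 and 3 to toxicity of the irradiated organ.
- A reader might infer that every group 3 hold of 14 to 28 days is handled in opposite ways. Many events already stop treatment under other 7.3.4 entries, such as related non-skin events of Grade 3 or higher (laboratory abnormalities aside) and other Grade 4 events. Extensions for events unrelated to the drugs do not conflict either, because the 14-day entry covers drug-related toxicity only.

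**Conclusion.** The conflict is between 7.3.4 and 7.3.3, and it is real. It covers drug-related nivolumab/BMS-986156 holds of 14 days or more that are not stopping events on other grounds, for example some Grade 3 skin events, some laboratory abnormalities and lower-grade events. It is clearest from 14 to 28 days. Beyond 28 days it depends on whether the 7.2.1 entry still bars restart after the DLT window.

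The documents give no frequency of such holds. Among the 20 planned group 3 patients the number affected could be anywhere from none upward, and I make no estimate. The conclusion assumes that the unsigned 14 days means at least 14 and that dosing follows the stated 28-day schedule.

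The 7.2.1 entry is a secondary matter. Its figure differs from 14 days without contradicting it, and it has no effect inside the 29-day window.

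**What to change.** The sponsor should make three wording changes for nivolumab/BMS-986156.

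1. Reconcile the hold limits in 7.3.3 and 7.3.4 and state which section prevails when both apply. This should cover the investigator's extensions and the omission of a dose, say whether an omitted dose counts as time blocked by toxicity, and add the missing inequality sign.
2. Align the entry of more than 28 days in 7.2.1 with the reconciled limit, or explain why it differs.
3. State how that entry counts when the group 3 DLT window closes on the day dose 2 is due, and whether it bars restart after the window.

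The limit itself is for the sponsor to set. The cost is a protocol amendment of wording only; sample size and analysis do not change.
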